* CTD³ may also be CTD for patients that will continue on the extension stage of the study.

³ Each study visit from cycle -1 to EOS has a +/- 3 day window. End of study visit should be at least 30 days after patient stops taking study medications.

*** these tests will be performed when clinically indicated and not on each visit and not more frequently than every 6 months

 RESEARCH RELATED
 STANDARD OF CARE

Appendix 3 MPN-SAF Symptom Assessment Package

Myeloproliferative Neoplasm Symptom Assessment Form (MPN-SAF)

Instructions: Please fill out all questions, as best able, reflecting how these symptoms affected you over the LAST WEEK unless directed otherwise. Complete forms until the STOP instruction toward the end of the packet.

Symptom	1 to 10 (0 if absent) ranking* 1 is most favorable and 10 least favorable
Please rate your fatigue (weariness, tiredness) by circling the one number that best describes your fatigue right NOW	(No Fatigue) 0 1 2 3 4 5 6 7 8 9 10 (Worst Imaginable)
Please rate your fatigue (weariness, tiredness) by circling the one number that best describes your USUAL Level of fatigue during past 24 hours	(No Fatigue) 0 1 2 3 4 5 6 7 8 9 10 (Worst Imaginable)
Please rate your fatigue (weariness, tiredness) by circling the one number that best describes your WORST level of fatigue during past 24 hours	(No Fatigue) 0 1 2 3 4 5 6 7 8 9 10 (Worst Imaginable)
Circle the one number that describes how, during the past 24 hours, fatigue has interfered with your	
• General Activity	(Does not Interfere) 0 1 2 3 4 5 6 7 8 9 10 (Completely Interferes)
• Mood	(Does not Interfere) 0 1 2 3 4 5 6 7 8 9 10 (Completely Interferes)
• Walking ability	(Does not Interfere) 0 1 2 3 4 5 6 7 8 9 10 (Completely Interferes)
• Normal Work (includes work both outside the home and daily chores)	(Does not Interfere) 0 1 2 3 4 5 6 7 8 9 10 (Completely Interferes)
• Relations with other people	(Does not Interfere) 0 1 2 3 4 5 6 7 8 9 10 (Completely Interferes)
• Enjoyment of life	(Does not Interfere) 0 1 2 3 4 5 6 7 8 9 10 (Completely Interferes)

Circle the one number that describes how, during the past Week how much difficulty you have had with each of the following symptoms	
Filling up quickly when you eat (Early Satiety)	(Absent) 0 1 2 3 4 5 6 7 8 9 10 (Worst Imaginable)
Abdominal pain	(Absent) 0 1 2 3 4 5 6 7 8 9 10 (Worst Imaginable)
Abdominal discomfort	(Absent) 0 1 2 3 4 5 6 7 8 9 10 (Worst Imaginable)
Inactivity	(Absent) 0 1 2 3 4 5 6 7 8 9 10 (Worst Imaginable)
Problems with Headaches	(Absent) 0 1 2 3 4 5 6 7 8 9 10 (Worst Imaginable)
Problems with Concentration - Compared to prior to my MPD	(Absent) 0 1 2 3 4 5 6 7 8 9 10 (Worst Imaginable)
Dizziness/ Vertigo/ Lightheadedness	(Absent) 0 1 2 3 4 5 6 7 8 9 10 (Worst Imaginable)
Numbness/ Tingling (in my hands and feet)	(Absent) 0 1 2 3 4 5 6 7 8 9 10 (Worst Imaginable)
Difficulty sleeping	(Absent) 0 1 2 3 4 5 6 7 8 9 10 (Worst Imaginable)
Depression or sad mood	(Absent) 0 1 2 3 4 5 6 7 8 9 10 (Worst Imaginable)
Problems with Sexual Desire or Function	(Absent) 0 1 2 3 4 5 6 7 8 9 10 (Worst Imaginable)
Cough	(Absent) 0 1 2 3 4 5 6 7 8 9 10 (Worst Imaginable)
Night Sweats	(Absent) 0 1 2 3 4 5 6 7 8 9 10 (Worst Imaginable)
Itching (pruritus)	(Absent) 0 1 2 3 4 5 6 7 8 9 10 (Worst Imaginable)
Bone Pain (diffuse not joint pain or arthritis)	(Absent) 0 1 2 3 4 5 6 7 8 9 10 (Worst Imaginable)
Fever (>100 F)	(Absent) 0 1 2 3 4 5 6 7 8 9 10 (Daily)
Unintentional weight loss last 6 months	(Absent) 0 1 2 3 4 5 6 7 8 9 10 (Worst Imaginable)
What is your Overall Quality of Life?	(As good as it can be) 0 1 2 3 4 5 6 7 8 9 10 (As Bad as it can be)

Appendix 4: Dynamic International Prognostic Scoring System (DIPSS)

The DIPSS is calculated as follows:

- Age >65 years: 1 point
- Leukocyte count >25,000/microL: 1 point
- Hemoglobin <10 g/dL: 2 points
- Circulating blast cells ≥1 percent: 1 point
- Presence of constitutional symptoms: 1 point

Subjects with zero, one to two, three to four, or 5 to 6 points were considered low, intermediate-1, intermediate-2, or high risk, respectively

Prognostic Variable	Value		
	0 Points	1 Point	2 Points
Hemoglobin	≥ 10 g/dL		< 10 g/dL
Age, years	< 65	≥ 65	
White blood cell count	≤ 25 x 10 ³ /uL	> 25 x 10 ³ /uL	
Peripheral blood blasts	< 1%	≥ 1%	
Constitutional symptoms	No	Yes	

Appendix 5: Subject Study Pill Diaries

PRIME: 12-1225
Subject Dosing Diary (Ruxolitinib)

Patient ID #						
Study Doctor Name:						
Study Doctor Phone Number:						

 • Take RUXOLITINIB twice daily approximately 12 hours apart (morning and evening). Swallow the pills and do not chew them. • All doses may be taken with or without food. Each dose should be taken with a glass of water. Avoid grapefruit juice and Seville (sour) oranges during the entire study. • If you forget to take a dose of RUXOLITINIB, take your dose within 3 hours after the missed dose. After 3 hours, that dose should not be taken. • If you vomit any doses of study drug DO NOT take another dose. • Do not start any new medication including over-the-counter medications. All medications must be approved by your physician. • Be sure to bring your diary, pill bottles and all leftover pills with you for all of your return appointments. Thank you. 						
RUXOLITINIB: You should take the following pills by mouth, with water, 12 hours apart						
	pills in the morning			pills in the evening		
Cycle ____	Date (DD/MM/YYYY)	Time Morning Dose	Time Evening Dose	Number of Pills	Side Effect or Question I Have	Time Noticed Side Effect
1	____ / ____ / ____	____	____	____	____	____ : AM / PM
2	____ / ____ / ____	____	____	____	____	____ : AM / PM
3	____ / ____ / ____	____	____	____	____	____ : AM / PM
4	____ / ____ / ____	____	____	____	____	____ : AM / PM
5	____ / ____ / ____	____	____	____	____	____ : AM / PM
6	____ / ____ / ____	____	____	____	____	____ : AM / PM
7	____ / ____ / ____	____	____	____	____	____ : AM / PM
8	____ / ____ / ____	____	____	____	____	____ : AM / PM
9	____ / ____ / ____	____	____	____	____	____ : AM / PM
10	____ / ____ / ____	____	____	____	____	____ : AM / PM
11	____ / ____ / ____	____	____	____	____	____ : AM / PM
12	____ / ____ / ____	____	____	____	____	____ : AM / PM
13	____ / ____ / ____	____	____	____	____	____ : AM / PM

PRIME: 12-1225
Patient Dosing Diary (Calendar Combo-Weekly)

Patient ID #

Study Doctor Name:	
Study Doctor Phone Number:	

- Take RUXOLITINIB twice daily approximately 12 hours apart (morning and evening). Swallow the pills and do not chew them.
- Take PANOBINOSTAT three times per week each week at the same time on each day **with the morning dose of RUXOLITINIB**. Swallow the capsules and do not chew them.
- All doses may be taken with or without food. Each dose should be taken with a glass of water. Avoid grapefruit juice and Seville (sour) oranges during the entire study.
- If you forget to take a dose of RUXOLITINIB, take your dose within 3 hours after the missed dose. After 3 hours, that dose should not be taken.
- If you forget to take a dose of PANOBINOSTAT, take your dose within 12 hours after the missed dose. After 12 hours, that day's dose should not be taken.
- If you vomit any doses of study drug DO NOT take another dose.
- Do not start any new medication including over-the-counter medications. All medications must be approved by your physician.
- Have Loperamide (Imodium) readily available in case you develop diarrhea. Contact [name] at onset of diarrhea. If the diarrhea does not improve on Loperamide or if you're having more than 4 stools per day (soft to watery in large amounts), contact [name] at [contact].
- Be sure to bring your diary, pill bottles and all leftover pills with you for all of your return appointments. Thank you.

RUXOLITINIB: You should take the following pills by mouth, 12 hours apart

_____ pills in the morning _____ pills in the evening

PANOBINOSTAT: You should take the following capsules by mouth, 3 times per week, every week

_____ capsules in the morning

Cycle_____ DAY	Date (DD/MM/YYYY)	Time Morning Dose	Time Evening Dose	Number of Pills/ Capsules	Side Effect or Question I Have	Time Noticed Side Effect
1 Ruxolitinib & Panobinostat	____ / ____ / ____	____	____	Rux: ____ Pan: ____		____ : AM / PM
2 Ruxolitinib	____ / ____ / ____	____	____	Rux: ____		____ : AM / PM
3 Ruxolitinib & Panobinostat	____ / ____ / ____	____	____	Rux: ____ Pan: ____		____ : AM / PM
4 Ruxolitinib	____ / ____ / ____	____	____	Rux: ____		____ : AM / PM
5 Ruxolitinib & Panobinostat	____ / ____ / ____	____	____	Rux: ____ Pan: ____		____ : AM / PM
6 Ruxolitinib	____ / ____ / ____	____	____	Rux: ____		____ : AM / PM
7 Ruxolitinib	____ / ____ / ____	____	____	Rux: ____		____ : AM / PM
8 Ruxolitinib & Panobinostat	____ / ____ / ____	____	____	Rux: ____ Pan: ____		____ : AM / PM

PRIME: 12-1225
Patient Dosing Diary (Calendar Combo-QOW)

Patient ID #

Study Doctor Name:	
Study Doctor Phone Number:	

- Take RUXOLITINIB twice daily approximately 12 hours apart (morning and evening). Swallow the capsules and do not chew them.
- Take PANOBINOSTAT three times per week every other week at the same time on each day with the morning dose of RUXOLITINIB. Swallow the capsules and do not chew them.
- All doses may be taken with or without food. Each dose should be taken with a glass of water. Avoid grapefruit juice and Seville (sour) oranges during the entire study.
- If you forget to take a dose of RUXOLITINIB, take your dose within 3 hours after the missed dose. After 3 hours, that dose should not be taken.
- If you forget to take a dose of PANOBINOSTAT, take your dose within 12 hours after the missed dose. After 12 hours, that day's dose should not be taken.
- If you vomit any doses of study drug DO NOT take another dose.
- Do not start any new medication including over-the-counter medications. All medications must be approved by your physician.
- Have Loperamide (Imodium) readily available in case you develop diarrhea. Contact [name] at onset of diarrhea. If the diarrhea does not improve on Loperamide or if you're having more than 4 stools per day (soft to watery in large amounts), contact [name] at [contact].
- Be sure to bring your diary, pill bottles and all leftover pills with you for all of your return appointments. Thank you.

RUXOLITINIB: You should take the following pills by mouth, 12 hours apart

_____ pills in the morning _____ pills in the evening

PANOBINOSTAT: You should take the following capsules by mouth, 3 times per week, every other week

_____ capsules in the morning

Cycle DAY	Date (DD/MM/YYYY)	Time Morning Dose	Time Evening Dose	Number of Pills/ Capsules	Side Effect or Question I Have	Time Noticed Side Effect
1 Ruxolitinib & Panobinostat	____ / ____ / ____	____	____	Rux: ____ Pan: ____		____ : AM / PM
2 Ruxolitinib	____ / ____ / ____	____	____	Rux: ____		____ : AM / PM
3 Ruxolitinib & Panobinostat	____ / ____ / ____	____	____	Rux: ____ Pan: ____		____ : AM / PM
4 Ruxolitinib	____ / ____ / ____	____	____	Rux: ____		____ : AM / PM
5 Ruxolitinib & Panobinostat	____ / ____ / ____	____	____	Rux: ____ Pan: ____		____ : AM / PM
6 Ruxolitinib	____ / ____ / ____	____	____	Rux: ____		____ : AM / PM
7 Ruxolitinib	____ / ____ / ____	____	____	Rux: ____		____ : AM / PM

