6.1.1 Dosing administration

RUXOLITINIB is administered orally BID everyday in a 28-day treatment cycle (Q4wk). Induction phase dose is 10 mg PO BID. In the combination phase, the starting dose of RUXOLITINIB is 10 mg and may be increased to 15mg PO BID. See [Table 6-1](#), [Table 6-2](#) for dose and treatment schedules.

PANOBINOSTAT is administered orally TIW, QOW, or QW in a 28-day cycle depending on the assigned cohort. Starting dose of PANOBINOSTAT is 10mg TIW QOW and may be increased to 20mg TIW QW depending on the assigned cohort. See [Table 6-1](#) for dose and treatment schedules.

Patients may take RUXOLITINIB and PANOBINOSTAT without regard to food. However, once the patient has made a choice (e.g., take drug after breakfast or at fasting), it is recommended that patient will follow the election choice consistently throughout the protocol.

On Day -28, the first dose of RUXOLITINIB only will be administered at the clinical site. First dose of PANOBINOSTAT will start on Cycle 1 Day 1 administered with the RUXOLITINIB morning dose at the clinical site. See [Table 6-2](#) for provisional escalating dose levels.

Table 6-1 Dose and treatment schedule

Study treatments	Pharmaceutical form and route of administration	Escalating Doses	Frequency and/or Regimen
RUXOLITINIB	Oral	10,15 mg	Twice daily, 28-day cycles
PANOBINOSTAT	Oral	10, 15 mg	Three times a week, every other week, 28-day cycles OR Three times a week, every week, 28 day cycle To be taken with the AM dose of RUXOLITINIB

Patients will self-administer RUXOLITINIB and PANOBINOSTAT as instructed as follows:

- RUXOLITINIB will be orally administered BID (approximately 12 hours apart: morning and evening)
- PANOBINOSTAT should be taken orally TIW (e.g. day 1, 3, and 5) at the same time on each day with the AM dose of RUXOLITINIB. Doses should be separated by a minimum of 30 hours within the week of dosing

- Dose may be taken with or without food
- Each dose of study drug should be taken with a glass of non-carbonated water (approximately 8 ounces/240ml). Patients should be instructed to swallow the capsules/tablets whole and not chew them.
- Patients must avoid grapefruits, grapefruit juice, pomegranate, starfruit, starfruit juice, Seville oranges and Seville orange juice during the entire study treatment period

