6.5 Study drug supply

6.5.1 Study drug preparation and dispensation

Both RUXOLITINIB and PANOBINOSTAT capsules including instructions for administration, will be dispensed by site study personnel on an outpatient basis. Patients will be provided with adequate supply of study drug for self-administration at home until at least their next scheduled study visit.

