Multiple ketoconazole doses at 400 mg increased C_{max} and AUC of PANOBINOSTAT by 1.6- and 1.8-fold, respectively, but with no change in T_{max} or half-lives in 14 cancer patients. The less than 2-fold increase in PANOBINOSTAT AUC upon co-administration of a strong CYP3A inhibitor is considered a weak drug inhibition and not clinically relevant, as PANOBINOSTAT doses at least 2-fold greater than the evaluated 20 mg dose (i.e., 40 mg and 60 mg) have been safely administered in patients. Thus, co-administration of PANOBINOSTAT with a moderate or weak CYP3A inhibitor is allowed. However, clinical monitoring of signs and symptoms of PANOBINOSTAT treatment related adverse events is recommended when long-term (≥ 1 week) concomitant administration of any strong CYP3A inhibitors and PANOBINOSTAT is medically indicated or investigated in a clinical study.

RUXOLITINIB is metabolized in the liver predominantly by the CYP3A4 isozyme. With concomitant dosing of potent CYP3A4 inhibitors such as those medications listed in [Table 3-1](#), plasma exposure of RUXOLITINIB increases approximately 2-fold. Use of those medications listed in [Table 3-1](#) is strongly discouraged, and investigators should consider alternative therapies wherever possible. However, if the use of a potent CYP3A4 inhibitor is necessary for the sake of the patient's safety, then a dose reduction of ~50% of RUXOLITINIB is mandatory. See [Section 6.3.4](#) for further details of this dose reduction schema.

Based on the low overall bioavailability of topical ketoconazole, with very low systemic levels seen following topical administration, no dose adjustment of RUXOLITINIB is needed for use with topical ketoconazole. No dose adjustments are necessary when RUXOLITINIB is co-administered with erythromycin, or by extension, with other moderate or weak inhibitors of CYP3A4, including grapefruit juice.

Patients with impaired liver function (as defined by NCI CTEP criteria)¹ are recommended not to receive PANOBINOSTAT concomitantly with strong CYP3A inhibitors because potential interaction has not been established in this population.

Table 3-1 Medications which are known strong CYP3A4/5 inhibitors to be used with caution

Macrolide antibiotics*
• telithromycin
• troleandomycin
Antifungals (azoles)
• ketoconazole
• itraconazole
• posaconazole
• voriconazole
Antidepressants
• nefazodone
HIV protease inhibitors:
• indinavir
• nelfinavir
• ritonavir
• saquinavir
• lopinavir
Miscellaneous drugs or products

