• ² Star fruit and pomegranate product and juice
• conivaptan

* azithromycin and regular orange juice are allowed.

Although clarithromycin is a known strong CYP3A inhibitor, it is also known to prolong QT intervals which is listed in [Table 2-1](#) and is prohibited to be taken with PANOBINOSTAT. This drug is thus not listed again in [Table 4-1](#).

This is not a comprehensive list of medications which may inhibit CYP3A4/5. The above list was compiled by using information listed under “draft guidance for industry, drug interaction studies, CDER 2006”, Indiana University School of Medicine drug interaction tables at <http://medicine.iupui.edu/clinpharm/DDIs/ClinicalTable.asp>, and “drug interaction database” from University of Washington. Additional updated versions with moderate and weak CYP3A inhibitors, which are meant to be used as a guide, may be found at the following website: <http://medicine.iupui.edu/clinpharm/DDIs/ClinicalTable.asp>.

D. Medications which are known CYP2D6 substrates to be used with caution

PANOBINOSTAT was also shown to be a CYP2D6 inhibitor (K_i 0.17 μM) *in vitro*. Thus, clinical drug-drug interaction study with PANOBINOSTAT as CYP2D6 inhibitor and dextromethorphan as CYP2D6 substrate was recently conducted in study [CLBH589B2109].

Multiple PANOBINOSTAT doses increased C_{max} and AUC of dextromethorphan by a mean of 1.8- and 1.6-fold respectively, but with no change in T_{max} in 17 cancer patients. An approximately 2-fold increase in dextromethorphan AUC upon co-administration with PANOBINOSTAT indicated that *in vivo* CYP2D6 inhibition of PANOBINOSTAT is weak.

As the study was conducted using a sensitive CYP2D6 substrate which resulted in a weak inhibition, drugs with a large therapeutic index such as anti-emetics, anti-hypertensives, and anti-depressants are generally safe to be co-administered with PANOBINOSTAT.

Patients should be carefully monitored for potential signs and symptoms of toxicity and may require dose titration or dose reduction of a sensitive CYP2D6 substrate which also have a narrow therapeutic window (e.g., the ratio of toxicity exposure ≤ 2 -fold higher than the efficacious or therapeutic exposure).

Table 4-1 Medications which are known CYP2D6 substrates to be used with caution

Beta blockers (listed below):	Antipsychotics (listed below):
S-metoprolol	aripiprazole
propafenone	haloperidol
timolol	risperidone
Antidepressants (listed below):	Antiarrhythmics (listed below):
amitriptyline	thioridazine

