clomipramine	mexiletine
desipramine	flecainide
imipramine	Others (listed below):
fluoxetine	codeine
paroxetine	dextromethorphan
venlafaxine	tamoxifen
duloxetine	tramadol
Antiemetics (listed below):	
ondansetron [^]	

[^]Intravenous dolasetron is a CYP2D6 substrate and contraindicated for preventing nausea and vomiting associated with chemotherapy based on FDA drug safety communication dated December 17, 2010. Please see [Table 2-1](#).

This is not a comprehensive list of CYP2D6 substrates. Additional updated versions of this list, which are meant to be used as a guide, may be found at the following website: <http://medicine.iupui.edu/clinpharm/DDIs/ClinicalTable.asp>

E. Medications which are known to be moderate inducers of CYP3A4 are to be used with caution

During the study, the use of moderate CYP3A4 inducers (e.g. bosentan, efavirenz, etravirine, modafinil, nafcillin, ritonavir, talviraline, tipranavir) is discouraged, and investigators should seek alternatives where possible. No dose adjustment will be used when moderate CYP3A4 inducers are co-administered with RUXOLITINIB. However, any concomitant use of moderate CYP3A4 inducers must be documented.

This is not a comprehensive list of medications which may induce CYP3A4/5. The above list was compiled by using information listed under “draft guidance for industry, drug interaction studies, CDER 2006”, Indiana University School of Medicine drug interaction tables at <http://medicine.iupui.edu/clinpharm/DDIs/ClinicalTable.asp>, and “drug interaction database” from University of Washington.

References (available upon request)

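### The food line in all three patient diaries omits whole grapefruit, pomegranate and star fruit, which section 6.1.1 bars throughout treatment

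*Combined protocol and SAP*

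**What the plan says.** Section 6.1.1 (Dosing administration) states the rule: "Patients must avoid grapefruits, grapefruit juice, pomegranate, starfruit, starfruit juice, Seville oranges and Seville orange juice during the entire study treatment period". It belongs to a list introduced by "Patients will self-administer RUXOLITINIB and PANOBINOSTAT as instructed as follows".

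Appendix 5 contains three diaries: ruxolitinib alone, the weekly combination calendar and the every-other-week combination calendar. All three carry the same food sentence: "Avoid grapefruit juice and Seville (sour) oranges during the entire study".

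Appendix 1, part C, Table 3-1 is titled "Medications which are known strong CYP3A4/5 inhibitors to be used with caution". Its only food entry is "Star fruit and pomegranate product and juice"; every other entry is a drug. The text before the table deals with grapefruit juice separately. It says ruxolitinib needs no dose adjustment with erythromycin or "other moderate or weak inhibitors of CYP3A4, including grapefruit juice".

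**The concern.** The diary is the written instruction that the patient takes home, and on food it is narrower than the mandatory rule it should convey. The gap also falls on the wrong items: the sentence keeps grapefruit juice, which Appendix 1 ranks as moderate or weak, and leaves out both foods that Appendix 1 ranks as strong.

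What is at stake is ruxolitinib exposure. Section 6.3.4 prohibits strong CYP3A4 inhibitors in Cycle 1 and makes a ruxolitinib reduction of about 50% mandatory if one becomes necessary later. A patient who does not know that star fruit or pomegranate matters has no prompt from the diary to avoid it or report it.

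**Working it through.** No sample size, power or error rate is involved. The check compares the texts item by item.

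**Inputs.** The food rule in section 6.1.1; the food sentence in each Appendix 5 diary; Table 3-1 and the surrounding text of Appendix 1, part C.

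**Step 1: the rule against the diaries.** The three diary sentences are identical, so one column serves for all.

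| Item barred in 6.1.1 | Diary sentence |
|---|---|
| Grapefruit (whole) | Not named |
| Grapefruit juice | Named |
| Pomegranate | Not named |
| Star fruit | Not named |
| Star fruit juice | Not named |
| Seville orange | Named |
| Seville orange juice | Not named, but can be read as covered by the fruit |

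By item: 2 named + 1 arguably covered + 4 missing = 7.

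By fruit: 1 named (Seville orange) + 1 named as juice only (grapefruit) + 2 absent (pomegranate, star fruit) = 4.

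**Step 2: whether another diary line fills the gap.** The other instructions cover dose timing, taking doses with or without food, water, missed doses, vomiting, new medications and returning the diary and pills. The combination diaries add loperamide. None restricts a particular food. The ban on starting new medications does not reach fruit.

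**Step 3: where the omitted foods stand in Appendix 1.** Foods in Table 3-1: 2 (star fruit, pomegranate). Of these, named in the diaries: 0. Grapefruit juice, which the diaries name, is not in the table. The Appendix 1 reference list includes a paper titled "Potent inhibition by star fruit of human cytochrome P450 3A (CYP3A) activity". Only the title is available here, so it shows why the entry is there and nothing about either study drug.

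**Step 4: what the documents say about exposure.** For ruxolitinib, section 6.3.4 and Appendix 1 part C give roughly a 2-fold rise with strong inhibitors as a class; section 1.3.4 reports an approximate doubling of AUC with ketoconazole. For panobinostat, Appendix 1 part C reports a 1.8-fold AUC with ketoconazole and regards it as weak and without clinical relevance. Neither drug has a figure for star fruit or pomegranate, and nothing says how often patients eat them.

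**Step 5: whether the omission looks deliberate.** The other diary instructions follow section 6.1.1 closely: the 12-hour spacing, the 3-hour and 12-hour missed-dose limits, and no repeat dose after vomiting. The diaries evidently put 6.1.1 into patient language, and no reason is given for a shorter food list.

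**The case against.** The strongest case is that the diaries omit something but do not contradict the rule. They nowhere permit pomegranate, star fruit or whole grapefruit. Section 6.1.1 governs and frames its list as what patients are told. Section 6.5.1 adds that the drugs, "including instructions for administration, will be dispensed by site study personnel". Other patient materials not available here may carry the full list. All of this stands as a limit on the consequence: it cannot be said that patients never receive the full rule. It does not make the written form correct.

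A second argument is that the documents are not uniform. Table 3-1 is headed as a caution list, part C prohibits its entries outright only in the first cycle, and part A of the same appendix carries another study's code, which suggests carried-over text. But section 6.1.1 is the trial's own rule on these foods and covers the whole treatment period. A milder heading in an appendix does not relax it, and the diaries would be short of 6.1.1 even if Table 3-1 were set aside.

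Third, the evidence of hazard is thin. The 2-fold figure is not specific to food, whole grapefruit is not classified at all, and Seville orange, which the diaries keep, is not classified either. This is right, and it is why the point is graded minor. The contrast between strong and weaker inhibitors applies only to star fruit and pomegranate against grapefruit juice.

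Finally, the copy reviewed cuts off the later daily log rows of each diary. The food sentence is complete in all three, and the missing parts appear to be log rows, so this does not change the reading.

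**Conclusion.** The inconsistency is real. All three diaries give a narrower food instruction than section 6.1.1: of four barred fruits, one is named, one is named as juice only and two are missing. The two missing fruits are the only foods that the protocol lists as strong CYP3A4/5 inhibitors.

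Severity is minor. The possible consequence is higher ruxolitinib exposure in a patient who relies on the diary. Its size cannot be estimated from the documents, and the class figure of about 2-fold should not be read as an estimate for these fruits. No effect on dose-escalation decisions, endpoints or analysis is claimed. The conclusion assumes that 6.1.1 states the intended rule. It does not assume that the diary is the patient's only source of instruction.

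**What to change.** In all three Appendix 5 diaries, replace the food sentence with:

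*Avoid grapefruit and grapefruit juice, pomegranate (fruit, juice and products), star fruit and star fruit juice, and Seville (sour) oranges and their juice during the entire study.*

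This covers every item in section 6.1.1. Naming pomegranate juice and products goes slightly beyond 6.1.1 and matches the scope of Table 3-1. Section 6.1.1 needs no change.

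The cost is one replaced sentence in three forms and a reissue with IRB approval. It adds no patients, visits or procedures.
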